### **5.3 INCLUSION CRITERIA**

- 1) Patients presenting with STEMI for PCI (characterized by chest discomfort, and prominent ST-segment elevation)
- 2) Patients presenting with NSTEMI (characterized by chest discomfort, raised levels of myocardial enzymes and/or ST-segment depression or prominent T wave inversion)
- 3) Able to give verbal consent (STEMI patient's pre procedure) and/or written consent (STEMI after procedure and NSTEMI patients prior to enrolment).
- 4) Age > 18 years of age
- 5) Able to take Aspirin and either prasugrel or ticagrelor.
- 6) Have no concurrent septic or inflammatory illness
- 7) Thienopyridine naive

### **5.4 EXCLUSION CRITERIA**

- 1) Be unable to provide verbal and written consent
- 2) Allergic to aspirin or any of the P2Y12 antagonists in the trial
- 3) Have pre-existing cardiogenic shock
- 4) Have a concurrent septic or inflammatory disease e.g. rheumatoid arthritis, lupus, pneumonia.
- 5) Already taking a P2Y12 inhibitor
- 6) Known bleeding diathesis
- 7) Patients **over** 75 years of age or under 60 kg or those who have had a previous stroke/transient ischaemic attack, will not be eligible for prasugrel but rather ticagrelor.
- 8) Patients with a history of intracranial haemorrhage will not receive prasugrel or ticagrelor but rather will receive treatment with clopidogrel.

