## **5. PARTICIPANT ENTRY**

### **5.1 CONSENT**

Consent will be a 2 stage process for patients undergoing PPCI for STEMI. Because the drugs given will be as per local and national recommended guidelines, consent will be verbal prior to the PPCI and first 3 blood samples. A shortened patient information sheet will be read to the patient (so as not to delay urgent treatment) and if verbal consent is gained it will be recorded in the clinical notes and the site file consent record. This is in line with NRES guidelines that suggest that patients admitted with STEMI are considered as unconscious patients initially.

Following emergency PCI when the patient is pain free and has been able to rest, a full patient information sheet will be proffered and written consent sought. If the patient does not want to be part of the trial the previous samples will be discarded and the data not used for analysis. Treatment will continue in accordance with clinical guidelines. The patients' participation in the trial will end with the 4hr sample.

For patients with UA/NSTEMI full written consent will be taken after the patient has read the full patient information sheet. Blood tests will be taken at time-points which coincide with STEMI time-points (20 minutes, 60 minutes, and 4 hours post dosage)

Patient Data will be anonymised and stored on RWHT trust fully encrypted computers

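### In the STEMI ticagrelor group, eligibility turns on giving written consent after dosing and PPCI, and the plan does not say how patients who die or lose capacity first are counted

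*Combined protocol and SAP*

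**What the plan says.** For STEMI patients, section 5.1 (Consent) says that "consent will be verbal prior to the PPCI and first 3 blood samples". Section 6.2.1 has ticagrelor given after that verbal consent. The second stage comes later: "Following emergency PCI when the patient is pain free and has been able to rest, a full patient information sheet will be proffered". The patient's signature is requested at that stage, and no deadline is set for it. The patient's part in the study ends with the 4-hour sample.

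For the other groups, section 5.1 says: "For patients with UA/NSTEMI full written consent will be taken after the patient has read the full patient information sheet". Section 6.2.2 places dosing after that written consent.

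The rule for a STEMI patient who does not go on is written for refusal: "If the patient does not want to be part of the trial the previous samples will be discarded and the data not used for analysis". Section 5.5 (Withdrawal Criteria) disposes of samples and erases data for patients who decide to withdraw, in any group.

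The entry criteria are worded in two ways. Inclusion criterion 3 (section 5.3) begins "Able to give verbal consent (STEMI patient's pre procedure) and/or written consent", and then places written consent after the procedure for STEMI and before enrolment for NSTEMI. Exclusion criterion 1 (section 5.4) is "Be unable to provide verbal and written consent", which asks for both.

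Section 4.1 lists death and TIMI major and minor bleeding as safety endpoints to be recorded for each participant.

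**The concern.** An entry criterion should be settled before exposure. For Group 5, the written half of exclusion 1 can be settled only after the drug has been given, blood taken and the procedure done, so meeting it depends partly on how the patient fared. A patient who gives verbal consent, is dosed and sampled, and then dies or stays too unwell to sign has neither declined nor withdrawn. The only text that reaches this patient is exclusion 1, and it removes them.

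Two things are at stake. The first is the safety description: a death, or a bleed in a patient who never regains capacity, falls outside the set of participants for whom endpoints are tabulated, and the reader of the results would not know. The second is objective 2, which asks whether STEMI itself reduces the effect of ticagrelor by comparing Groups 5 and 6. Section 2.2 expects hypotension and diverted gut blood flow to slow absorption. Patients who deteriorate after dosing plausibly have more of both, so losing them from Group 5 would make STEMI look closer to NSTEMI.

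**Working it through.** **The plan's own figure.** Three groups of 15 (section 5.2) give 3 × 15 = 45, which matches section 6.1. The plan states no alpha, power, effect size, SD or dropout rate, so there is no power calculation to reproduce.

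**The same event in the two groups.**

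| Step | Group 5 (STEMI) | Group 6 (NSTEMI) |
|---|---|---|
| Consent before dosing | Verbal | Full written |
| Dose and first samples | On verbal consent | On written consent |
| Written consent | After PCI, once pain free and rested | Already given |
| Patient declines or withdraws | Removed (5.1, 5.5) | Removed (5.5) |
| Patient dies or loses capacity after dosing | Not addressed in 5.1 or 5.5; removed if exclusion 1 is applied as written; arguably kept under inclusion 3 | Stays in |

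The difference is confined to the last row. Withdrawal erases data in every group, so that route is not one-sided.

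**Chance that it arises.** The documents give no loss rate, so f, the proportion lost between dosing and written consent through death or incapacity, is assumed. With 15 STEMI patients dosed, P(at least one lost) = 1 − (1 − f)^15:

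- f = 2%: 26%
- f = 5%: 54%
- f = 10%: 79%
- f = 15%: 91%

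**Effect on the death count.** If one of 15 verbally consented patients dies before written consent and is dropped, the table shows 0 of 14 instead of 1 of 15 (6.7%). If that patient is replaced, it shows 0 of 15 instead of 1 of 16 (6.3%).

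**Effect on mean platelet reactivity.** Suppose that the patients lost are exactly the worst fraction f of a normal reactivity distribution. The mean of those kept is then too low by φ(z)/(1 − f) SD, where z is the (1 − f) quantile of the standard normal and φ its density. If the condition that causes loss correlates with reactivity at ρ, multiply by ρ.

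| Assumed f | Shift, ρ = 1 (upper bound) | Shift, ρ = 0.5 |
|---|---|---|
| 5% | 0.109 SD | 0.054 SD |
| 10% | 0.195 SD | 0.097 SD |
| 15% | 0.274 SD | 0.137 SD |

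**Scale.** The standard error of a 15 v 15 difference in means, with a common SD, is √(2/15) = 0.365, or about 0.37 SD. The largest shift in the table is 0.274/0.365 = 0.75 of one standard error. At an assumed 80% power and two-sided 5%, the detectable difference is 0.365 × (1.960 + 0.842) = 1.02 SD.

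**The case against.** The strongest reply is that the plan never says that such patients are removed. The discard rule is for patients who do not want to take part, the withdrawal rule for those who decide to leave, and exclusion 1 is an entry criterion, not a rule for deleting data. Inclusion 3, with its and/or, can be read as letting verbal consent suffice for STEMI. This stands in part: removal after death or incapacity is inferred from exclusion 1. But the two criteria then point in opposite directions for the same patient, and nothing else in the plan decides between them.

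A reader might infer that a STEMI death before written consent can never be counted. The documents do not support that. Section 9.2 requires all adverse events to be reported, section 9.2.2 requires information on all serious events to be collected, and neither is conditional on written consent. What is unclear is whether the death reaches the endpoint table.

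A reader might also infer that the sickest patients are removed from the STEMI side alone. That goes too far. Pre-existing cardiogenic shock is excluded in every group, and NSTEMI patients too ill to read the information sheet and sign never enter. What is peculiar to Group 5 is selection after dosing. Since written consent has no deadline, a patient who is unwell for a time can still give it later, which leaves mainly deaths and lasting incapacity.

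Nor can the point be extended to the prasugrel comparison. Objective 1 uses STEMI data already collected, and the consent route of that cohort is not described.

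Finally, this is a pilot that is not powered for clinical outcomes, and the shift in the mean is below one standard error even in the worst case shown. That is right. It rules out calling this a serious bias in the platelet results, but it does not answer the point about patient flow and safety counts.

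**Conclusion.** The point holds for Group 5 against Group 6. Exclusion 1, combined with written consent after the procedure, makes STEMI eligibility depend on the patient's course after dosing, and sections 5.1, 5.3 and 5.4 are not reconciled on what follows. The main consequence is for reporting: applied as written, exclusion 1 takes a post-dose STEMI death or loss of capacity out of the analysed group and out of the death and bleeding endpoints, without any line in the results to show it.

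The effect on mean platelet inhibition is secondary. It probably runs towards no STEMI effect, provided that the patients lost are those with poorer absorption, and is at most about 0.11 to 0.27 SD. That range rests on an assumed 5 to 15% loss, normality, and losses falling wholly on the worst responders; a correlation of 0.5 halves it. Two-stage consent is not itself at fault, since the plan adopts it so as not to delay urgent treatment. The point should be acted on, but it does not undermine the design.

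**What to change.** 1. Keep a non-identifying tally of every verbally consented STEMI patient who does not reach written consent, by reason: declined, died, too unwell. Report it in the patient flow, and count deaths from verbal consent. No sample data are used. Section 5.1 already provides for verbal consent to be entered in a site file consent record, and section 5.5 for withdrawals to be logged, so the cost is one log line and one row in the flow diagram.

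2. Reword exclusion 1 and inclusion 3 so that they agree, and so that removal of samples and data applies to patients who decline or withdraw. This is a protocol amendment needing ethics approval.

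Whether data from patients who died or lost capacity after verbal consent may be kept is for the ethics committee. I have not seen the text of section 10.1 (Ethics Approval), so any condition there should be checked first. Item 1 stands whatever the committee decides.

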### **5.5 WITHDRAWAL CRITERIA**

Patients who decide to withdraw their consent to participate in the study will have all samples collected up to the time of withdrawal disposed of in appropriate manner. All information collected on the patient for the purpose of the study shall be erased. The withdrawal shall be recorded in the study patient identification log. The treatment of the patient will continue in accordance with clinical guidelines should the participant chose to withdraw or not.

## **6. ASSESSMENT AND FOLLOW-UP**

**6.1 Subjects:** A total of 45 subjects will be included in the study of which 15 patients will undergo PPCI as part of the treatment for STEMI.

### **6.2 Sampling**

**6.2.1 STEMI patients** will have a P2Y12 inhibitor administered (ticagrelor as per current local and national guidance) following verbal consent. The time of loading dose will be recorded and the patient transferred to the cardiac catheterization suite. After the insertion of the radial or femoral sheath, 15 ml of whole blood will be drawn from this sheath at 20 minutes post dosing (or as close to this time point as practicable) and also at the first balloon inflation time. A further 15 ml will be taken at 60 minutes post dosing (or as close as is practicable). Further sampling on the ward will take place after 4 hours post dosing from an antecubital vein using a 21 gauge needle (see appendix 2 for a flow chart summarizing procedure for these groups).

**6.2.2 NSTEMI patients** will have a P2Y12 inhibitor administered (prasugrel or ticagrelor) following full written consent. The time of loading dose will be carefully recorded. 15 ml of blood will be taken at 20 minutes, 60 minutes and then 4 hours post dosing solely from an antecubital vein using a 21 gauge needle (see appendix 3 for a flow chart summarizing procedure for these groups).

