## 1. LAY SUMMARY

Major heart attacks are caused by a number of factors, the two major of which are furring up of a coronary artery with atheroma and then sudden clot formation on this area leading to a blockage and interruption of blood flow. The clots that lead to heart attacks are largely made of clotting blood cells (platelets) that in health repair blood vessels and inhibit spontaneous bleeding. One of the main treatment strategies for heart attacks is to make these cells less “sticky”. Aspirin is a main stay of treatment at our institution and in addition one of three other antiplatelet agents acting on the same platelet activation pathway (P2Y12 receptor) are used (clopidogrel, prasugrel or ticagrelor). When a patient is admitted with a major heart attack, they are treated with emergency primary percutaneous coronary intervention (PPCI) a technique where a wire and balloon are used to reopen the coronary artery and then usually a stent (a slotted metal tube) is placed to keep the artery open. Aspirin and one of the P2Y12 inhibitor agents are given to prevent further clots and all have been shown to reduce negative events following heart attacks and angioplasty with stent insertion.

All three P2Y12 inhibitor agents are taken in tablet form immediately before the emergency PPCI procedure. It appears that these agents in healthy stable patients take at least 30 min to 2 hours to have an adequate effect. In PPCI patients, often the procedures are performed well within this timescale. Furthermore patients who are having a heart attack may not have normal drug absorption with blood being diverted away from the stomach and gut activity being suppressed by other drugs such as morphine.

In this study patients with major heart attacks will be given one of the three anti-platelet agents (being treated as per normal clinical pathways). Blood samples will be taken to assess the effect of the anti-platelet agents when the balloon opens the artery and after 20 minutes, 60 min and 4 hours after taking the drugs.

A variety of tests will be used to check the activity of the drugs including measuring the concentration of the active component of each of the three anti-platelet agents in the blood.

In total the patients in the study will require up to 4 extra blood tests, each using 15 ml of blood (approximately 3 teaspoons of blood). This will not cause any ill effects but may involve up to 3 extra needle pricks.

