## 2.2 RATIONALE FOR CURRENT STUDY

It is unlikely that gastro intestinal absorption during a STEMI is equivalent to that of a resting patient. Hypotension and or diversion of splanchnic blood flow is likely to slow drug absorption and the intrinsic increase in platelet activity seen during STEMI (22, 23) may also inhibit the antiplatelet effect of drugs. A previous pharmacokinetic study has shown reduced drug absorption during STEMI (24). In the current study we aim to demonstrate whether prasugrel, or ticagrelor are having a significant clinical effect *during* the primary angioplasty (STEMI patients), and investigate the pharmacodynamic properties of these agents in the setting of STEMI. By also studying patients with unstable angina (UA)/NSTEMI we will investigate whether the condition of STEMI *per se* affects the pharmacodynamics of these agents.

A number of methods have been developed to assess the effect of P2Y12 receptor inhibition. Their effect is probably best measured using techniques that specifically measure P2Y12 ADP receptor activation, such as vasodilator stimulated phosphoprotein phosphorylation (VASP) and the VerifyNow P2Y12 system (Accumetrics, San Diego, CA) (24). We will utilize both of these methods in this study. We will also measure aspirin activity using the VerifyNow aspirin test.

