### **3. STUDY OBJECTIVES**

- 1) To determine the degree and time-course of platelet inhibition in patients admitted with NSTEMI treated with prasugrel within the first 4 hours of loading. These data will be compared with data already collected on STEMI patients treated with prasugrel to determine whether the condition of STEMI per se reduces the efficacy of prasugrel treatment.
- 2) To demonstrate the degree and time-course of platelet inhibition by ticagrelor given acutely before emergency primary angioplasty for STEMI, during the procedure and in the following 4 hours. This will be compared with a cohort of patients presenting with NSTEMI treated with ticagrelor to determine whether the condition of STEMI per se reduces the efficacy of ticagrelor treatment.

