## 4. STUDY DESIGN

This is a pilot study which is both non-randomised and observational in nature. We plan on recruiting a total of 45 participants into the study who will comprise of patients admitted to New Cross Hospital suffering from an acute coronary syndrome. The study will complete an on-going project (REC ref no. 13/WM/0025 ethical approval granted from South Birmingham Regional Ethics Committee). Whole blood samples will be taken from participants following a single loading dose of an antiplatelet agent once the diagnosis of an ACS has been made. We anticipate the conclusion of subject recruitment in 3 months from the study start date

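### No pre-dose PRU or PRI is taken in the three recruited groups, so a post-dose STEMI–NSTEMI difference cannot by itself show that STEMI reduces the drug's efficacy

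*Combined protocol and SAP*

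**What the plan says.** Section 3 sets two objectives of the same form. For ticagrelor, STEMI and NSTEMI patients are compared "to determine whether the condition of STEMI per se reduces the efficacy of ticagrelor treatment". For prasugrel the aim is worded the same way, but only the NSTEMI group is recruited here: "These data will be compared with data already collected on STEMI patients treated with prasugrel". Section 4 states: "This is a pilot study which is both non-randomised and observational in nature".

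Section 6.2 gives the sampling.
- **NSTEMI (6.2.2):** "15 ml of blood will be taken at 20 minutes, 60 minutes and then 4 hours post dosing solely from an antecubital vein".
- **STEMI (6.2.1):** the loading dose is given and timed before transfer to the catheter suite. Then "15 ml of whole blood will be drawn from this sheath at 20 minutes post dosing", or as near to that time as can be managed, with another draw at first balloon inflation. Next, "A further 15 ml will be taken at 60 minutes post dosing (or as close as is practicable"), and a last venous draw on the ward after 4 hours.

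The lay summary lists the same times: "when the balloon opens the artery and after 20 minutes, 60 min and 4 hours after taking the drugs". In the schedule table closing section 6.3.3, the pre-dosing column holds consent and nothing else.

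Sections 6.3.1 and 6.3.2 report PRU and % PRI as levels at each time. Section 7 names generic parametric and non-parametric tests, with no baseline term and no change from baseline. Active-metabolite concentration is outcome (c) in section 4.1 and is measured in the same samples.

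On untreated platelets, section 2.2 says that "the intrinsic increase in platelet activity seen during STEMI (22, 23) may also inhibit the antiplatelet effect of drugs".

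**The concern.** Efficacy of a P2Y12 inhibitor is how far it lowers platelet reactivity. The study measures where reactivity ends up, not where it started. The protocol's own rationale names intrinsic platelet activity as something that changes in STEMI, and the groups are defined by diagnosis, so equal starting levels cannot be assumed.

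If untreated reactivity differs between STEMI and NSTEMI, the post-dose comparison carries that difference with it. Depending on its direction, the study could report reduced efficacy where the drug works equally well, or miss a real reduction. Both objectives are written to draw exactly this conclusion.

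**Working it through.** **1. Is any reading pre-dose?** The lay summary states up to 4 blood tests per patient. Counting from section 6.2:
- STEMI: 20 min + balloon + 60 min + 4 h = 4, which reproduces the stated maximum.
- NSTEMI: 20 min + 60 min + 4 h = 3.
- The STEMI dose precedes transfer, so the balloon sample is also post-dose.
- Pre-dose readings: 0 of 4 and 0 of 3. The schedule table agrees. The flow charts in Appendices 2 and 3 were not visible in the text reviewed.

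This covers the groups recruited here: 3 × 15 = 45, as stated. The sampling schedule of the earlier STEMI prasugrel data is not described.

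**2. What does a post-dose difference contain?** Write R = U − E, where U is untreated reactivity and E is the lowering due to drug. With S for STEMI and N for NSTEMI,

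R_S − R_N = (U_S − U_N) − (E_S − E_N).

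One quantity is observed and two are unknown. If the drug instead removes the same fraction I in both groups, R_S − R_N = (U_S − U_N)(1 − I). The untreated gap then shrinks as inhibition deepens, so the problem is likely largest at the early samples. It may also be smaller for PRI than for PRU, because section 6.3.2 derives PRI from paired incubations of the same sample. Untreated PRI is still unmeasured.

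**3. How large could it be?** The documents give no SD, untreated shift, alpha or power. Assume a two-sample t-test, two-sided 5%, n = 15 per group and identical drug effect. Let d be the part of the untreated shift that reaches the reading, in SD units with the SD held fixed. The noncentrality is d × √(15/2), with 28 degrees of freedom. For d = 0.50 it is 0.50 × 2.739 = 1.369, giving 26%.

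| Share of shift carried | Shift 0.25 SD | 0.50 SD | 0.75 SD |
|---|---|---|---|
| All | 10% | 26% | 51% |
| Half | 6% | 10% | 17% |
| One fifth | 5% | 6% | 7% |

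The nominal rate is 5%. The choice of model matters. A proportional-inhibition simulation (20,000 runs; assumed untreated mean 5 SD and added noise of 0.5 SD) gives 9 / 21 / 43% with no inhibition and 8 / 15 / 29% at 50% inhibition for the same three shifts.

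The 15 v 15 setting fits ticagrelor. The number of earlier STEMI prasugrel patients is not stated.

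**4. Can concentration settle the question?** The half-width of the 95% CI for a group difference is t(0.975, 28) × √(2/15) = 2.048 × 0.365 = 0.748, or about ±0.75 SD. A non-significant concentration difference therefore does not rule out reduced absorption.

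The analyte also needs defining. Section 2.1 says that ticagrelor is not a prodrug, while sections 4.1 and 6.3.3 name only its active metabolites.

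**The case against.** The strongest reply is that section 2.2 treats raised intrinsic activity as one route by which STEMI blunts the drug. On that reading it belongs to the effect of STEMI and is not contamination. If the objective means only that on-treatment reactivity is higher in STEMI for whatever reason, the comparison answers it. This stands as far as it goes, but section 3 speaks of the drug's efficacy and does not adopt that meaning. Even on that reading, a different starting level and a weaker drug response remain indistinguishable.

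Second, PRU and PRI are not the whole plan: concentrations are a named outcome, and Cmax and AUC are planned. That is right, and a reader should not infer that exposure is ignored. What is missing is a commitment in section 7 to report exposure beside reactivity, and concentrations do not supply an untreated reading.

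Third, this is a declared observational pilot. That limits what is expected of it, but the objectives still state a causal conclusion.

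Two stronger readings are tempting and are not supported.
- A reader might infer that every reading in the study is post-dose. The already-collected STEMI prasugrel data are not described well enough to say so. Even if they hold a pre-dose value, the NSTEMI prasugrel group has none, so no baseline-adjusted contrast is possible.
- A reader might infer that untreated reactivity is higher in STEMI than in NSTEMI, so that the bias runs towards finding reduced efficacy. Section 2.2 mentions an increase in STEMI but makes no comparison with NSTEMI. The direction is unknown.

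**Conclusion.** The point holds for the three groups recruited under this protocol. With no pre-dose PRU or PRI and no randomisation, a post-dose STEMI–NSTEMI difference in either direction cannot by itself separate drug effect from untreated reactivity, yet section 3 would use it to decide on efficacy.

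The missing draw is certain; the size of its effect is not. The rates of 10 / 26 / 51% rest wholly on assumed shifts carried fully into the reading, and they fall towards 5% as inhibition deepens. They show that the problem could matter at early samples, not that it does. The comparison remains valid as a description of on-treatment reactivity. This should be fixed, and it can be fixed in the text.

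**What to change.** **Section 3.** State that the STEMI–NSTEMI comparison is of on-treatment platelet reactivity (PRU, PRI) and drug concentration, and that reduced efficacy or reduced absorption will not be concluded from PRU or PRI alone.

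**Section 7.** Commit to reporting, within each drug at 20 min, 60 min and 4 h, the STEMI–NSTEMI difference with 95% CI in measured concentration beside those in PRU and PRI. Report AUC only over the time points that both groups share. Define the analyte for each drug, including whether parent ticagrelor is measured. Note that concentration need not track inhibition at the same moment, especially for prasugrel, and that at 15 per group a non-significant concentration difference does not exclude reduced absorption.

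**Do not adjust PRU or PRI for concentration to rescue the efficacy claim.** In a 200,000-run simulation with assumed inputs (raw PRU difference 0.75 SD, concentration–PRU correlation 0.5 / 0.7), an equal mix of causes left both the concentration difference and the adjusted PRU difference non-significant in 39 / 52% of studies. With untreated level as the only cause and an assumed 1 SD sampling-site effect on measured concentration, the pair pointed wrongly to absorption in 68 / 71%.

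**Limits to state.** The 20-minute sample comes from a sheath in the STEMI ticagrelor group but from a vein in NSTEMI. For Objective 1, say whether the earlier STEMI prasugrel data include a pre-dose reading.

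**Cost.** No new sample or procedure; a more modest conclusion and a little more analysis. The change does not supply the missing baseline. It keeps the conclusion within what the data can support.
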